11.0 Safety Analyses

Safety analyses will be presented for subjects in the full analysis set.

As this is a non-drug interventional study, only serious adverse events that the investigator considers reasonably related to interventional study procedures (i.e., venipunctures) or those considered reasonably related to ABT-530 and/or ABT-493 drug exposure in the prior study by the investigator will be reported as serious adverse events.

Collected adverse events will be coded using the Medical Dictionary for Regulatory Activities (MedDRA) and tabulated by system organ class (SOC) and preferred term (PT).

11.1 Analysis of Adverse Events

11.1.1 Tabulations of Serious Adverse Events

Serious adverse event data will be summarized and presented using primary MedDRA SOCs and PTs according to the version of the MedDRA coding dictionary used for the study at the time of database lock. The actual version of the MedDRA coding dictionary used will be noted in the clinical study report. The SOCs will be presented in alphabetical order and the PTs will be presented in alphabetical order within each SOC.

Subjects reporting more than one AE for a given PT will be counted only once for that term. Subjects reporting more than one AE within an SOC will be counted only once for that SOC. Subjects reporting more than one AE will be counted only once in the overall total.

A summary of serious adverse events by SOC and PT will be generated.

11.1.2 Listing of Adverse Events and Deaths

Listings of all serious (as defined in the protocol) adverse events and deaths (from the time the subject signed the study-specific informed consent through the end of the study) will be provided.

11.2 Analysis of Medical Events Related to Liver Disease or HCV Infection

Any events related to liver disease progression and/or HCV infection that are considered to be clinically significant by the investigator and begin or worsen after Day 1 will be captured on the appropriate Medical Events eCRF(s). These significant events include but are not limited to: the development of cirrhosis, events indicative of hepatic decompensation, changes in Child-Pugh classification, liver transplantation, hepatocellular carcinoma, and/or death.

The number and percentage of subjects who reported each and any of the following medical events will be summarized:

ABT-493/ABT-530
M13-576 – Statistical Analysis Plan
Version 1.0 – 23 Aug 2019

- development of cirrhosis,
- hepatic decompensation variceal bleeding,
- hepatic decompensation new ascites,
- hepatic decompensation spontaneous bacterial peritonitis,
- hepatic decompensation hepatic encephalopathy,
- hepatic decompensation hepato-renal syndrome,
- hepatic decompensation hepatic hydrothorax,
- other evidence of hepatic decompensation,
- change in the Child-Pugh category,
- hepatocellular carcinoma,
- occurrence of liver transplantation,
- death.
- other.

Listings of each medical event will be provided. In addition, listings of any liver diagnostic testing that is collected (e.g., liver biopsy or FibroScan scores) will be provided.

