### **Recording Medical Events Related to Liver Disease, HCV Infection or the Event of Death**

Any events (i.e., diagnoses) related to liver disease progression and/or HCV infection that are considered to be clinically significant by the investigator and begin or worsen after Day 1 will be captured on the appropriate Medical Events eCRF until the end of the study or initiation of re-treatment for HCV (if applicable). Significant events related to liver disease progression include the development of cirrhosis, events indicative of hepatic decompensation, (including: variceal bleeding, new ascites, spontaneous bacterial peritonitis, hepatic encephalopathy, hepato-renal syndrome, hepatic hydrothorax or other evidence of hepatic decompensation considered to be significant by the investigator), change in the Child-Pugh category (e.g., change from Child-Pugh Class A to Child-Pugh Class B), the occurrence of hepatocellular carcinoma, liver transplantation and/or death.

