**Appendix C. Study Activities A and B**

**Table A. SVR and Non-SVR Subjects Not Receiving Re-Treatment**

Activity	Day 1 a	Month 3 b,c	Month 6 b,c	Month 12 b,c	Month 18 b,c	Month 24 b,c	Month 30 b,c	Month 36 b,c
Informed Consent	X							
Medical History (related to liver disease/HCV infection) including past HCV drug treatments (during the prior study and before prior study)	X							
Assessment of Medical Events Related to Liver Disease/HCV Infection		X	X	X	X	X	X	X
Child-Pugh Score and Classification (cirrhotic subjects only) d	X		X	X	X	X	X	X
INR	X		X	X	X	X	X	X
Serum Albumin	X		X	X	X	X	X	X
IP-10 Sample	X	X	X			X	X (if final visit)	X
Clinical Chemistry Tests including Fibro Test and APRI (see Table 1 for details)	X	X	X	X f	X f	X	X (if final visit)	X
Platelets (for APRI)	X	X	X			X	X (if final visit)	X
HCV RNA Sample	X	X	X	X	X	X	X	X
HCV Resistance Sample	X	X	X	X	X	X	X	X
Archive Plasma Sample	X	X	X	X	X	X	X	X
Collection of Liver Diagnostic Results	X	X	X	X	X	X	X	X
HCC Screening Liver ultrasound for subjects with cirrhosis only (at Final visit only)	X g	X g	X g	X g	X g	X g	X g	X g

Activity	Day 1 a	Month 3 b,c	Month 6 b,c	Month 12 b,c	Month 18 b,c	Month 24 b,c	Month 30 b,c	Month 36 b,c
Assess for SAE related to Study Procedures or to Exposure to ABT-493 and/or ABT-530 in the prior study	X	X	X	X	X	X	X	X
Documentation of Medications for the Treatment of HCV or Treatment of an SAE Related to Study Procedures or to Exposure to ABT-493 and/or ABT-530 in the Prior Study	X	X	X	X	X	X	X	X
Collection of re-treatment regimen information and dosing dates (if applicable) e		X e	X e	X e	X e	X e	X e	X e

- a. The interval between the last dose of DAA therapy in the prior AbbVie clinical study and the Day 1 Visit of Study M13-576 must be no longer than 2 years.
- b. Once a subject has reached approximately 3 years post-DAA therapy, participation in Study M13-576 will be completed. The study visit which falls closest to 3 years since the subject's last dose of AbbVie DAA will be registered as their final visit.

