4.1 Objectives

The primary objectives of this study are as follows:

- Assess the durability of response for subjects who achieved SVR₁₂ with a regimen including ABT-493 and/or ABT-530.
- Assess the persistence of specific HCV amino acid substitutions associated with drug resistance in subjects who experienced virologic failure.

The secondary objectives of the study are as follows:

• Summarize medical events related to progression of liver disease including but not limited to events of hepatic decompensation, change in Child-Pugh classification, liver transplantation, hepatocellular carcinoma, and/or death.

• Summarize results of the following laboratory tests and scores: FibroTest, APRI, IP-10, alpha fetoprotein (if collected under a protocol version prior to protocol Amendment 3), FibroScan, and liver biopsy.

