11.3 Analysis of Laboratory Data

Data collected from the central and local laboratories, including additional laboratory testing due to an SAE, will be used in all analyses.

Hematology variables include: platelet count

Chemistry variables include: total bilirubin, alpha-fetoprotein, gamma glutamyl transferase (GGT), alpha2-macroglobulin, AST, ALT, haptoglobin, and apolipoprotein A1.

Additional variables include: FibroTest, IP-10, INR, and serum albumin.

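### SAP 11.2 summarises change in Child-Pugh class only from investigator-reported events and leaves the scheduled Child-Pugh scores unanalysed, so a scored but unreported worsening is not counted

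*SAP*

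**What the plan says.** The secondary objective in SAP 4.1 reads "Summarize medical events related to progression of liver disease including but not limited to events of hepatic decompensation, change in Child-Pugh classification", followed by further liver outcomes. Protocol Sections 4.0 and 5.3.3.1 name the same item.

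Two data streams bear on it:

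- **Scheduled scores.** Protocol Appendix C, Table A has a row "Child-Pugh Score and Classification (cirrhotic subjects only"), marked at Day 1 and at Months 6, 12, 18, 24, 30 and 36. Note d extends scoring to every cirrhotic subject, including those who become cirrhotic on study, once Amendment 2 is approved at the site.
- **Reported events.** SAP 11.2 takes its data from the Medical Events eCRF. Capture there is confined to events tied to progression or to HCV, with this further condition: "considered to be clinically significant by the investigator and begin or worsen after Day 1". The planned analysis is: "The number and percentage of subjects who reported each and any of the following medical events will be summarized". One item on that list is "change in the Child-Pugh category".

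The laboratory analysis in SAP 11.3 covers total bilirubin among the chemistry variables and adds: "Additional variables include: FibroTest, IP-10, INR, and serum albumin". SAP 11.3.1 gives descriptive statistics by visit for each parameter. Under SAP 5.1 and 11.0 the safety analyses use the full analysis set.

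**The concern.** The study collects a repeated, rule-based measure of the outcome in the subjects at risk, and the SAP makes no use of it. The summary depends on an investigator noticing a change in category, judging it clinically significant and entering it as an event. A subject whose scheduled scores move to a worse category without an eCRF entry appears in neither the Child-Pugh row nor the any-event total.

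Two smaller points attach to the same row. It does not say which direction of change it means. Its percentage is also taken over the full analysis set, which includes non-cirrhotic subjects who are never scored, so it does not describe the subjects in whom the outcome can be observed.

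At stake is the descriptive answer to one component of a secondary objective. No hypothesis test depends on it.

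**Working it through.** There is no plan figure to reproduce: the documents give no cirrhotic count, expected event count or power calculation for this outcome. The check has four steps.

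**1. Is the score analysed anywhere in the SAP?** Child-Pugh appears in SAP 4.1 (objectives) and SAP 11.2 (medical events) only. SAP 11.3 lists bilirubin, INR and albumin but neither the score nor the category. The listings of liver diagnostic tests in SAP 11.2 give biopsy and FibroScan as examples and do not name Child-Pugh. SAP 12.0, which records departures from the protocol, does not mention dropping the scores.

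**2. Could the by-visit laboratory summaries stand in for it?** No. They describe each component across subjects, so they cannot show one subject's category or a change in it. They also omit ascites and encephalopathy, two of the five items in Protocol Appendix E, Table 2.

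**3. Can the category worsen with no clinical decompensation event?** Apply Table 2 to assumed laboratory values, with no ascites (1 point) and no encephalopathy (1 point) throughout:

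| Item | Earlier visit | Points | Later visit | Points |
|---|---|---|---|---|
| Bilirubin, mg/dL | 1.9 | 1 | 2.0 | 2 |
| Albumin, g/dL | 3.6 | 1 | 3.5 | 2 |
| INR | 1.1 | 1 | 1.1 | 1 |
| Ascites + encephalopathy | none | 2 | none | 2 |
| Total (category) | | 5 (A) | | 7 (B) |

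More generally, with both clinical items at 1 point, the three laboratory items give totals from 3 × 1 + 2 = 5 to 3 × 3 + 2 = 11. With cut-offs of 5–6 for A, 7–9 for B and 10–15 for C, all three categories can be reached on laboratory values alone. A small shift such as the one in the table is the kind an investigator might reasonably not report, and the SAP would then not count it.

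**4. Direction and denominator.** Three categories give six ordered changes: three worsening (A to B, A to C, B to C) and three improving. The row's wording does not separate them. On the denominator, if the full analysis set were about the planned 400 subjects, one subject would be 1/400 = 0.25 percentage points. If, purely as an assumption, 10% to 30% of 400 were cirrhotic (40 to 120), the same subject would be 1/120 = 0.8 to 1/40 = 2.5 points among those scored. This shows how much the choice of denominator matters. It does not estimate how many changes are missed.

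**The case against.** A reader might infer from the undirected row that the SAP counts any reported change, so that a move from B to A would be tallied as progression. The documents do not support that. SAP 11.2 limits capture to progression or HCV-related events that start or get worse after Day 1. Protocol Section 5.3.1.1 places the item among significant progression events, and its only illustration is a worsening: "change in the Child-Pugh category (e.g., change from Child-Pugh Class A to Child-Pugh Class B"). Each medical event will also be listed, so a misdirected entry could be found. What remains is that an example is not a definition and that the objective itself speaks only of change.

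A second defence is that the SAP follows the protocol: Protocol 5.3.3.1 refers to Section 5.3.1.1, which sends category changes to the Medical Events eCRF. That is correct, and the point is not that the SAP contradicts the protocol. It is that a scheduled measure of a named secondary outcome has no planned analysis.

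A third defence is that the scores are incomplete. They start only after Amendment 2 approval at the site. At Month 30 the score is scheduled, but the chemistry panel that supplies bilirubin is drawn only if that is the final visit. Bilirubin at Months 12 and 18 entered the main schedule only with Amendment 3. This stands. It rules out calling the scores the more reliable source, and it rules out replacing the eCRF events with them: a subject with one score and a genuine reported worsening would then be lost. It is a reason to use both sources.

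**Conclusion.** The point holds as a gap in the analysis plan, of minor weight in a purely descriptive study. SAP 11.2 answers the Child-Pugh component of the secondary objective through discretionary event reporting alone, and a worsening that is scored but not reported is not counted. The missing direction is a matter of wording, because the context points to worsening. The full-analysis-set percentage dilutes an outcome that is scored only in cirrhotic subjects.

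The size cannot be estimated: the documents give neither the number of cirrhotic subjects nor any indication of how often scored changes go unreported. The conclusion assumes that the SAP text is complete on Child-Pugh, with no separate derivation specified elsewhere.

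**What to change.** In SAP 11.2:

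1. Define the row as worsening of Child-Pugh category (A to B or C, or B to C). Count a subject if the worsening is reported on the eCRF or is shown by the scheduled scores relative to the first available score in this study. Counting either source keeps reported worsening in subjects who have too few scores.
2. Add a shift table of category, from first available to worst and from first available to last, among cirrhotic subjects with at least two scores. State that denominator. Show improvement separately and keep it out of the any-event total.
3. List every subject for whom the scheduled scores and the eCRF events disagree.

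The cost is a short SAP revision and one derived variable from data the protocol already schedules; no visit or sample is added. The downside is coverage. Because of the gaps before Amendment 2 approval and at Month 30, the shift table will include fewer subjects than the number with cirrhosis, and for some early enrolees the first available score may fall well after Day 1. Both limits should be stated beside the table.

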11.3 Analysis of Laboratory Data

Data collected from the central and local laboratories, including additional laboratory testing due to an SAE, will be used in all analyses.

Hematology variables include: platelet count

Chemistry variables include: total bilirubin, alpha-fetoprotein, gamma glutamyl transferase (GGT), alpha2-macroglobulin, AST, ALT, haptoglobin, and apolipoprotein A1.

Additional variables include: FibroTest, IP-10, INR, and serum albumin.

11.3.1 Statistical Methods

Each protocol-specified laboratory parameter will be summarized at each applicable study visit (e.g., Day 1, Month 3, Month 6, etc. as defined in the protocol) with the sample size, visit mean, SD, minimum, median, and maximum.

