### **Clinical Laboratory Tests**

Samples will be obtained for the clinical laboratory tests, including FibroTest and APRI, IP-10, and quantitative HCV RNA PCR, INR and serum Albumin at the visits specified in [Appendix C](#) for all subjects, until the end of the study or initiation of re-treatment for HCV (if applicable).

A certified central laboratory will be utilized to process and provide results for the clinical laboratory tests.

Sites should refer to the laboratory manual provided by the central laboratory, AbbVie, or its designee for instructions regarding the collection, processing, and shipping of all laboratory samples. The certified laboratory chosen for this study is Covance. Depending on the location of the study site, samples will be sent initially to one of the following addresses, where the specimen will be analyzed or sent to a different location for analysis or storage:

Covance  
[name]  
[name]

Covance  
[name]  
[name]  
[name]

Covance  
[name]  
[name]  
[name]

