- c. Visit window interval. Study visits should ideally take place within 3 weeks of the planned visit date. If the Month 3 visit is more than 6 weeks later than planned it should be registered instead as the Month 6 visit. If a Month 6, 12, 18, 24, 30 or 36 visit is more than 12 weeks later than planned it should be registered as the next visit in the schedule.
- d. Child-Pugh Score and Category should be assessed on all cirrhotic subjects (those cirrhotic upon enrollment and those who become cirrhotic during the study) after approval of Amendment 2 at the site.
- e. Subjects who are virologic failures and begin a re-treatment regimen during participation in the Study M13-576 will begin following the Study Activities Table B for re-treated subjects at the time re-treatment begins.
- f. Total bilirubin only will be collected at Month 12 and Month 18 for the Child-Pugh Score for cirrhotic subjects only.
- g. HCC Screening Liver ultrasound will be performed on subjects with cirrhosis at the visit considered the Final visit for the subject, unless the subject has a liver ultrasound, CT or MRI performed for HCC screening within 3 months prior to that visit, in which case the result of that US, CT or MRI will be used as the result for Final Study Visit assessment.

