4.2 Study Design

This Phase 2/3, multicenter study will be conducted in subjects who received at least one dose of an ABT-493- and/or ABT-530-containing regimen at any dose level in a prior AbbVie Phase 2 or 3 study for the treatment of chronic HCV and elect to enroll in this study. The subject must have completed the follow-up period of the prior eligible AbbVie study. It is anticipated that approximately 400 subjects will participate in this study. An attempt will be made to enroll all virologic failures who will not receive immediate retreatment with a regimen containing ABT-493/ABT-530.

At the Day 1 Visit, subjects will provide written (signed and dated) informed consent prior to any study specific procedures being performed. The investigator will evaluate whether the subject meets all of the eligibility criteria prior to enrollment in this rollover study. Subjects will be followed for approximately 3 years following their last dose of DAA in the previous AbbVie HCV clinical study; the 3 years will be inclusive of any post-treatment period in the prior study, as well as any gap between the end of the prior study and enrollment into this study. Once a subject has reached 3 years post-DAA therapy, participation in this study will be completed, except for subjects enrolled with virologic failure who receive re-treatment with a new HCV antiviral regimen that does not contain ABT-493/ABT-530. Subjects who are re-treated with HCV regimens other than ABT-493/ABT-530 will have only one further assessment for treatment outcome 12 weeks after stopping that therapy or earlier in cases of virologic failure. Subjects who have not been re-treated will return to the study site for their scheduled visits on an outpatient basis as described in Section 5.3.1 of the protocol until approximately 3 years after their last dose of DAA in the previous clinical study.

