4.3 Sample Size

No sample size determination was conducted for this study. The objective of the study is to characterize the persistence of amino acid substitutions in subjects enrolled in AbbVie DAA studies who experienced virologic failure, and the durability of response in subjects who achieved SVR₁₂. Thus, the number of subjects enrolled in the current trial will be partially based on the number of subjects who experienced virologic failure in prior studies with AbbVie DAA therapies and subsequently agree to participate in the current trial.

The sample size was increased under protocol Amendment 2 to allow for inclusion of a representative sample of subjects from additional studies added in Amendment 2.

[figure not shown]

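### SAP 11.3.1 pools total bilirubin by visit, but Months 12 and 18 are drawn from cirrhotic subjects only, so the visit summaries are not comparable and can show a rise and fall that the schedule alone produces

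*SAP*

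**What the plan says.** The collection schedule is in Protocol Appendix C, Table A. The row "Clinical Chemistry Tests including Fibro Test and APRI (see Table 1 for details" is marked at Day 1 and Months 3, 6, 24 and 36, at Month 30 only when that is the subject's final visit, and at Months 12 and 18 with a pointer to note f. Table 1 of the protocol includes total bilirubin in that chemistry panel. Note f reads: "Total bilirubin only will be collected at Month 12 and Month 18 for the Child-Pugh Score for cirrhotic subjects only". Note d counts as cirrhotic, for Child-Pugh purposes, both subjects with cirrhosis at enrolment and subjects who develop it on study.

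The analysis is in the SAP. Section 11.3 states: "Chemistry variables include: total bilirubin, alpha-fetoprotein, gamma glutamyl transferase (GGT" and goes on to the rest of the panel. Section 11.3.1 states: "Each protocol-specified laboratory parameter will be summarized at each applicable study visit", giving sample size, mean, SD, minimum, median and maximum. Section 11.0 sets the population: "Safety analyses will be presented for subjects in the full analysis set". The SAP has no split of laboratory data by cirrhosis, no change from Day 1, and no footnote on the restricted visits. SAP 7.1 lists cirrhosis status, but only as a baseline characteristic carried over from the prior study.

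**The concern.** A by-visit table is read across its columns. Here the reader would pass from columns scheduled for cirrhotic and non-cirrhotic subjects together (Day 1 to Month 6), to two columns scheduled for cirrhotic subjects only (Months 12 and 18), and then to columns open to both groups again. A difference between neighbouring columns mixes any real change with a change in who was sampled, and the planned statistics cannot separate the two.

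Bilirubin is a component of the Child-Pugh score (Protocol Appendix E), and summarising liver disease progression is a secondary objective. A temporary rise in the mean could be read as worsening liver function after DAA therapy. Protocol 8.1.3 promises a summary of shifts in laboratory measurements, which would have exposed such an artefact, but SAP 11.3.1 contains no shift table or within-subject change. The list of changes from the protocol in SAP 12.0 does not mention the point.

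**Working it through.** There is no planned figure to reproduce. SAP 4.3 says "No sample size determination was conducted for this study", and neither document gives a bilirubin value.

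**Step 1: does the word applicable remove Months 12 and 18?** No. SAP 11.3.1 ties visits to the protocol's definition, Table A schedules bilirubin at both months, and SAP Table 2 gives each a window (days 272–451 and 452–631). The INR and serum albumin rows of Table A carry no cirrhotic-only note, so the problem is specific to bilirubin.

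**Step 2: inputs.**
- N = 400, from SAP 4.2: "It is anticipated that approximately 400 subjects will participate in this study".
- p, the cirrhotic share of enrolment: not given. Assumed 10–40%, borrowed from the background figure in Protocol 3.0 for chronic HCV in general.
- d, cirrhotic minus non-cirrhotic mean bilirubin: not given. Assumed 0–0.5 mg/dL. The documents support the direction only indirectly, in that higher bilirubin scores worse on Child-Pugh.
- m0, the non-cirrhotic mean: not given. It cancels.

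**Step 3: formula, with bilirubin constant within every subject.**
- Visit drawn from all subjects: mean = m0 + p × d.
- Visit drawn from cirrhotic subjects only: mean = m0 + d.
- Artefact = (m0 + d) − (m0 + p × d) = (1 − p) × d.

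**Step 4: results (mg/dL).**

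| p | d = 0 | d = 0.1 | d = 0.3 | d = 0.5 |
|---|---|---|---|---|
| 10% | 0.00 | 0.09 | 0.27 | 0.45 |
| 20% | 0.00 | 0.08 | 0.24 | 0.40 |
| 40% | 0.00 | 0.06 | 0.18 | 0.30 |

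The visit n would fall from about 400 to between 400 × 0.10 = 40 and 400 × 0.40 = 160, before dropout and completion.

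**Step 5: simulation check.** With 400 subjects, constant values, p = 20% and d = 0.3, one draw gave 63 cirrhotic subjects. The mean was 0.60 at Day 1 to Month 6, 0.86 at Months 12 and 18, and 0.60 at Month 24; the median went 0.56, 0.80, 0.56. With d = 0 there was no rise (means 0.55, 0.54, 0.55). The simulation kept all 400 subjects at Month 24, which the study will not do (Step 6).

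**Step 6: who is left at Month 24.** Subjects not previously re-treated may enrol up to 2 years after the last DAA dose (Protocol 5.2.1), and the final visit is the one closest to 3 years after that dose (Table A, note b). A subject who enrols g months after the last dose has about 36 − g months on study. Month 24 is the closest or a later visit only if 36 − g is at least 21, the midpoint of Months 18 and 24, so g must be at most about 15 months. Subjects who enrol later than that finish before Month 24. Month 24 and later columns are therefore also a subset, selected by enrolment timing rather than by cirrhosis.

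**The case against.** The strongest objections are these.

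- **A rise is not established.** A reader might infer that the table will show bilirubin going up and coming down. The documents do not support that: they give no bilirubin values and no cirrhotic share, and the artefact is zero if d = 0. This stands. What holds for any d is that the columns describe different populations.
- **Month 24 is not a return to the whole cohort.** A reader might take the later columns as describing everyone again. By Step 6 they do not, so a return to exactly the Day 1 level cannot be claimed. This stands.
- **The n of 40 to 160 is only p × 400.** It ignores dropout, completion and re-treatment. It also ignores that the Month 12 and 18 bilirubin entries came into the main protocol only with Amendment 3, after an earlier UK-only amendment. Actual numbers are likely to be smaller. This stands.
- **The table prints n at each visit.** A sharp drop would be visible, but nothing in the plan would explain it. This partly answers the concern.
- **The importance is limited.** Total bilirubin is not among the tests named in the objectives. Progression is summarised from subject-level events, including Child-Pugh category change and decompensation (SAP 11.2), which a pooled mean does not touch. With m0 = 0.5, even the largest assumed mean, 0.5 + 0.5 = 1.0 mg/dL, stays in the lowest Child-Pugh bilirubin band (below 2 mg/dL). This stands and sets the weight of the point.
- **Local and SAE-related results also enter the analysis (SAP 11.3).** A few non-cirrhotic values could therefore appear at Months 12 and 18. That does not restore comparability.

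**Conclusion.** The point holds in limited form. Followed as written, SAP 11.3.1 gives total bilirubin means and medians at Months 12 and 18 for essentially cirrhotic subjects, next to columns for a mixed population. That conclusion needs no assumption. A spurious rise and fall is possible if cirrhotic subjects have higher mean bilirubin: 0 to 0.45 mg/dL under the assumed ranges of p and d, neither of which comes from trial data.

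The documents do not support a reading that the study's conclusions on liver disease progression are compromised. One descriptive laboratory table is affected, and no primary endpoint or hypothesis test is. The point is worth acting on because the correction is cheap and the planned laboratory summaries contain nothing that would reveal the artefact.

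**What to change.** Amend SAP 11.3.1 for total bilirubin:

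1. Summarise it by cirrhosis status, and show no pooled mean or median at Months 12 and 18.
2. State how cirrhosis status is assigned. The prior-study baseline status in SAP 7.1 is not enough alone, because note d also covers subjects who become cirrhotic later. Count them in the cirrhotic group from onset, or show them separately, so that their Month 12 and 18 values are not dropped. Development of cirrhosis is already captured at Day 1 for the interval since the prior study (Protocol 5.3.1.1) and afterwards as a medical event (SAP 11.2).
3. Label the Month 12 and 18 columns as cirrhotic subjects only, and note that Month 24 and later include only subjects still in follow-up.

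Change from Day 1 in the same subjects would be a useful addition and would go some way towards the shift summary promised in Protocol 8.1.3. If nothing else is done, the footnote in item 3 should be added.

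The cost is a few SAP sentences, slightly more programming and a simple rule for on-study cirrhosis. No new data are needed. With case mix fixed within each group, the schedule artefact is zero for any p and d. Dropout and staggered completion can still change the mix at later visits.
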